Protocol Amendment 1, Version 2.0, dated 06FEB2018 added a 6-month open-label extension to allow subjects to receive ATI-50002 Topical Solution, 0.46%. In addition, to assist with enrollment and to facilitate enrollment of subjects less than 60 years of age, the amendment specified that after the first 6 subjects were enrolled in the study, the blood PK samples were no longer collected. Administrative Letters 1 through 5 were incorporated into Protocol Amendment 1. Administrative Letter #1 (dated October 2, 2017) outlined the change from a single center to a multicenter study, clarified that M689 would not be measured and that the method for the detection of ATI-50002 in the scalp was a qualified method. Administrative Letter #2 (dated December 19, 2017) added superficial tape stripping of the scalp biopsy site for pharmacokinetic analysis to remove any residual study medication in the upper layers of the stratum corneum prior to biopsy. Administrative Letter #3 (dated January 22, 2018) allowed for a decrease in the volume of study medication applied from 4 mL to 1.5 mL to 4 mL, and Administrative Letter #4 (dated January 29, 2018) updated the address for Aclaris Therapeutics, Inc. Administrative Letter #5 (dated 03AUG2018) clarified the treatment duration of the Open Label Extension (OLE) portion of the study for subjects with a gap between Visit 7 and entry into the OLE due to an administrative delay.

AMENDMENT RATIONALE:

The primary purpose of Amendment 2, Version 3.0 dated 14AUG2018 is to increase the duration of the open-label extension (OLE) to 12 months.

Protocol Version	Date	Section	Revision
Version 1.0	26JUL2017	NA	NA
Version 2.0	06FEB2018	Title page	Replaced single center with multicenter in the title and added 6-Month Long-term open label Extension
		Protocol Approval Signature Page	
		Investigator Signature Page	
		Synopsis	
		Title page	Removed [name]
		Title page	Updated the Medical Monitor to: [name], RAC
		Section 10.2.2, Procedure for Reporting Adverse Events	
		Synopsis, Number of Study Sites	Updated site number to two.
		Section 6.1, Number of Subjects	
		Synopsis, Study Design, Endpoints, Statistical Methods	Concentrations of M689 in the blood will not be measured.
		Section 7.1 Overall Study Design	
		Section 9.3.2 Blood Samples	
		Section 12.4 Pharmacokinetic Analysis	
		Synopsis: Endpoints section	Clarified that the bioanalytical methods for the skin biopsy are qualified and not fully validated methods.
		Section 9.3.1, Scalp Biopsy	Added tape stripping of the area of the scalp that will be biopsied for pharmacokinetic analysis with 5 D-Squame circular discs.
		Appendix 5, Scalp Biopsy	
		Synopsis: Study Design, Study Medication Administration	Changed the volume of study medication applied to the scalp from 4 mL to a minimum of 1.5 mL up to a maximum of 4 mL of study medication.
		Section 7.1 Overall Study Design	
		Section 8.3 Application of Study Medication	
		Appendix 1, Subject Instructions	

Protocol Version	Date	Section	Revision
		Synopsis, multiple sections Applicable sections throughout the protocol	Clarified Double-blind period and Added Open-Label Extension information, including additional visits, study medication and statistical analyses.
		Synopsis, Inclusion Criteria Section 6.3, Inclusion Criteria	Added Inclusion Criteria 11: Sexually active male subjects must agree to use a barrier method of contraception from the first application of study medication to at least 30 days after the last application of study medication.
		Synopsis, Exclusion Criteria Section 6.5.2, Prohibited and/ or Restricted Medications	Clarified Exclusion Criterion #15; JAK inhibitor exclusion is for both topical and oral. Clarified Exclusion Criterion #16; alopecia areata includes (AA, AU, AT)
		Section 3.1, Summary	Clarified the purpose of the study is to determine if topical application of ATI-50002 will result in regrowth of the scalp hair loss and if applicable, eyebrow hair loss due to AU and AT.
		Section 4.1, Study Rationale	Added a description of how subjects will enter the open label extension and nonclinical justification for 6-month treatment duration.
		Synopsis, Study Design, Statistical Methods Section 7.1, Overall Study Design Section 7.3, Schedule of Assessments Section 12.4, PK analyses	Added that only the first 6 subjects enrolled will have the pharmacokinetic blood samples will not be collected.
		Section 7.3, Schedule of Assessments	Update Table to reflect additional study visits for open-label extension.
		Section 8.8, Other Study Supplies	Added ECG equipment and supplies for PD samples.
		Section 8.10, Study Medication Packaging	Added subjects must complete double-blind treatment to be eligible for entry into the open-label extension, Clarified controlled room temperature conditions for study medication storage, Described open-label study medication supplies.
		Section 9.4, Eyebrow Assessments (Open-Label Extension)	Added the Clinician's Eyebrow Assessment and Subject's Eyebrow Assessments at Day 29 and monthly throughout the open-label extension period.
		Section 10.2.4.1, Study Medication Interruption	Replaced hold with interrupt and clarified that Study medication can be resumed after the abnormal laboratory value returns to normal or baseline, if in the opinion of the Investigator, it is in the best interest of the subject to continue.
		Section 11.2 Highly Effective Methods of Birth Control	Added Obstruction of fallopian tubes via medical device (Essure™).

Protocol Version	Date	Section	Revision
		Section 12.5.4 Secondary Analyses	Added efficacy and satisfaction analyses consistent with potential hair regrowth from longer treatment duration.
		Appendix 1, Subject Instructions for Study Medication Application to the Scalp	Added study subjects should avoid strenuous exercise that would cause profuse sweating for at least 6 hours after study medication application. Added instructions for avoidance of exposure of scalp to excessive natural or artificial ultraviolet radiation and sunscreen information.
		Appendix 2, Subject Instructions for Study Medication Application to the Eyebrow(s)	Added study medication instructions for subjects with eyebrow loss who are participating in the open-label extension.
		Appendix 3, Alopecia Areata History	Simplified the AA history
		Protocol	Minor editorial changes and corrections of typographical errors were made.
Version 3.0	14AUG2018	Synopsis Study Design Duration of Treatment Endpoints Study Medication Administration Section 4.1, Study Rationale Section 6.5.1 Permitted Concomitant Therapies and Over the Counter Products (OTC) Section 6.8, Subject Withdrawal criteria Section 7.1, Study Design Section 7.3, Schedule of Assessments Section 7.5, Duration of the Study Section 8.1, Investigational Study Medication Section 8.2, Subject Randomization Section 8.4, Study Medication Weights Section 8.5, Treatment Compliance Section 9.1.1, SALT Score Section 9.1.2, ALODEX Score Section 9.4, Eyebrow Assessments Section 9.4.1, Clinician's Eyebrow Assessment Section 9.4.2, Subject's Eyebrow Assessment Section 9.5.2, Physical Examination Section 9.5.3, Clinical Laboratory Assessments Section 9.5.4, Pregnancy Tests Section 9.6.2, Photographic Assessment	Revised the duration of open-label treatment from 6 months to 12 months and added two additional visits (Visit 15 and 16). Post-treatment follow-up Visit 14 is now Visit 16. Maximum duration of study participation is 400 days (393 + 7 days).

Protocol Version	Date	Section	Revision
		Synopsis, Efficacy Assessments Section 12.5.4, Secondary Analyses	Added Week 40 and 52 to the SALT, ALODEX, Subject Satisfaction, CEA and SEA analyses
		Section 3.1, Summary, Overview of Alopecia Areata	Revised statement from AA is “the most prevalent” to “a prevalent” autoimmune disease in the United States
		Section 4.2 Study Rationale	Removed “6 month update” from the 9-month minipig study with dermal administration since full 9-month report is completed. Added update from currently enrolled subjects.
		Section 8.7, Study Medication Accountability	Added language to allow sites with a written drug destruction/disposal policy to dispose of unused and used investigational product on-site rather than returning to Aclaris.
		Section 8.10 Study Medication Packaging, Labeling, Storage and Security	Revised number of bottles to be dispensed.

1. SYNOPSIS

Protocol Number: ATI-50002-AA-202	Protocol Title: Double-blind, Vehicle-controlled Multicenter Study to Evaluate the Safety, Tolerability, Pharmacokinetics and Pharmacodynamics of ATI-50002 Topical Solution Administered Twice-Daily for 28 Days in Adult Subjects with Alopecia Universalis and Alopecia Totalis with a 12-Month, Long-Term, Open-Label Extension
Sponsor: Aclaris Therapeutics Inc.	Phase of Development: Phase 2
Study Medication Description: ATI-50002 Topical Solution, 0.46% Vehicle Topical Solution	
Study Objectives: Primary: To assess safety, tolerability, pharmacokinetics and pharmacodynamics of ATI-50002 Topical Solution, 0.46% compared to vehicle in subjects with alopecia universalis (AU) and alopecia totalis (AT) Secondary Objectives: To assess the efficacy of ATI-50002 Topical Solution, 0.46% for the treatment of scalp hair loss and eyebrow in subjects with AU or AT. To assess subject satisfaction following treatment with ATI-50002 Topical Solution, 0.46% for the treatment of scalp hair loss in subjects with AU or AT.	
Study Design: During the double-blind period, this Phase 2, multicenter, randomized study is designed to evaluate the safety, tolerability, pharmacokinetics and pharmacodynamics of ATI-50002 Topical Solution in subjects with AU and AT. Subjects will be required to have a clinical diagnosis of stable, clinically typical, AU or AT for a duration of at least 6 months up to and including seven years. In the double-blind phase, a total of approximately 12 subjects will be randomized to a 2:1 ratio: 
 • ATI-50002 Topical Solution, 0.46%, BID for 28 days (8 subjects) • Vehicle Solution BID for 28 days (4 subjects) During the screening period, subjects will be assessed for eligibility into the study. Subjects who meet all the entry criteria will be randomized to ATI-50002 Topical Solution, 0.46% or Vehicle Topical Solution and will apply a minimum of 1.5 mLs up to a maximum of 4 mLs of study medication to the entire scalp twice-a-day (BID) for 28 days (except for Day 1 and Day 28 when study medication will only be applied once a day). For the first 6 subjects enrolled in the study, blood samples for concentrations of ATI-50002 will be collected on Day 1 (Visit 2) and Day 28 (Visit 6) at pre-dose and 1, 2, 4, 8 hours post dose and on Day 2 (Visit 3) and Day 29 (Visit 7) at 24 hours post-dose. Blood samples for immunology will be collected on Day 1 (Visit 2) before study medication application and on Day 29 (Visit 7), 24 hours after study medication application on Day 28 (Visit 6). A 4-mm punch biopsy of the scalp will be obtained to determine the concentration of ATI-50002 in the scalp skin on Day 2 (Visit 3) and on Day 29 (Visit 7) 24 hours after study medication application on Day 1 (Visit 2) and on Day 28 (Visit 6). A 4-mm punch biopsy will be obtained to determine histology and immunology, prior to study medication application on Day 1 (Visit 2) and on Day 29 (Visit 7), 24 hours after study medication application on Day 28 (Visit 6). Safety and tolerability will be evaluated	

at each study visit by assessment of adverse events and vital signs, and at select visits, ECGs and clinical laboratory tests will be completed.

Open-Label Extension:

On Day 29 (Visit 7) subjects who complete Visit 7, continue to meet the entry criteria, have no clinically significant AEs or tolerability issues and in the opinion of the investigator have experienced or are capable of re-growing scalp hair will be eligible to enter a 12-month open-label extension. In the open-label extension, safety, tolerability and efficacy will be assessed. All subjects enrolled in the open-label extension will apply ATI-50002 Topical Solution, 0.46% to the entire scalp, twice daily for 52 weeks (12 months). In addition, subjects with eyebrow loss may apply a thin film of study medication to the affected eyebrow(s) twice-daily for 52 weeks (12 months). Subjects will be followed for safety, tolerability and efficacy as detailed in Section 7.3. Subjects who decline or are not eligible for the open-label extension should be seen for the Visit 16 (Post-treatment) assessments 30 days following the Day 28 (Visit 6). The duration of the open-label extension (OLE) should be based on the date of the visit that the subject initiated OLE treatment rather than the days from Baseline (Visit 2). For subjects who entered the open-label extension and had a gap between Visit 7 and entry into the open-label extension due to an administrative delay total study participation may be longer than 400 days.

Number of Subjects (planned):

12 subjects will be enrolled into the study.

Number of Study Sites:

This study will be conducted at two clinical sites.

Inclusion Criteria:

Subjects must meet all the following criteria to be eligible for participation in the study.

1. Able to comprehend and willing to sign an Informed Consent Form (ICF).
2. Male or non-pregnant, non-nursing female ≥ 18 years old at the time of informed consent.
3. Have a clinical diagnosis of stable, clinically typical, alopecia universalis or alopecia totalis.
4. Have a duration of the current episode of AU or AT for a minimum of 6 months and a maximum of seven years.
5. Have $> 95\%$ total scalp hair loss as measured by the Severity of Alopecia Tool (SALT).
6. If a woman of childbearing potential (WOCBP), must have a negative serum pregnancy test at Screening (Visit 1) and a negative urine pregnancy test (UPT) at Baseline (Visit 2) and agree to: use a highly effective method of birth control for the duration of the study; not be planning a pregnancy during the study duration and use contraception for 30 days after last application of study medication (Refer to Section 11).
7. Be in good general health and free of any known disease state or physical condition which, in the investigator's opinion, might impair evaluation of the subject or which might expose the subject to an unacceptable risk by study participation.
8. Be willing and able to follow all study instructions and to attend all study visits.
9. Subjects taking hormonal replacement therapies must be on stable doses for 6 months prior to enrollment and remain on the same maintenance dose throughout the study.
10. Subjects taking thyroid replacement medication must be on stable doses for 6 months prior to enrollment and remain on the same maintenance dose throughout the study.
11. Sexually active male subjects must agree to use a barrier method of contraception from the first application of study medication to at least 30 days after the last application of study medication.

Exclusion Criteria:

Subjects are excluded from this study if any 1 or more of the following criteria is met:

1. Females who are nursing, pregnant, or planning to become pregnant for the duration of the study including 30 days after the last application of study medication.

2. Patchy alopecia areata, diffuse alopecia areata or a history of an atypical pattern of AA (e.g., ophiasis, sisaiopho).
3. Concomitant hair loss disorder (by history or physical exam) such as androgenetic alopecia or scarring alopecia (e.g., cicatricial alopecia, frontal fibrosing alopecia, etc.).
4. Active skin disease on the scalp (such as psoriasis or seborrheic dermatitis) or a history of skin disease on the scalp that in the opinion of the investigator would interfere with the study assessments of efficacy or safety.
5. Active scalp trauma or other condition affecting the scalp that, in the investigator's opinion, may affect the course of AU or AT or interfere with the study conduct or evaluations.
6. The presence of a permanent or difficult to remove hairpiece or wig that will, in the opinion of the investigator, interfere with study assessments if not removed at each visit.
7. History of or current severe, progressive or uncontrolled renal, hepatic, gastrointestinal, pulmonary, cardiovascular, genitourinary (renal disease) or hematological disease, neurologic or cerebral disorders, infectious disease or coagulation disorders that, as determined by the Investigator, would preclude participation in and completion of study assessments.
8. History of, current or suspected systemic or cutaneous malignancy and/or lymphoproliferative disease, other than subjects with a history of adequately treated and well healed and completely cleared non-melanoma skin cancers (basal or squamous cell carcinoma) treated successfully at least 1 year prior to study entry with no evidence of disease.
9. Evidence of active or latent bacterial (including tuberculosis) or viral infections at the time of enrollment, or history of incompletely treated or untreated tuberculosis. Subjects who have completed therapy for latent tuberculosis may participate.
10. History of a serious local infection (e.g., cellulitis, abscess) or systemic infection including but not limited to a history of treated infection (e.g., pneumonia, septicemia) within 3 months of baseline (Visit 2). Subjects on an antibiotic for a non-serious, acute local infection must complete the course prior to enrollment into the study.
11. Positive for HIV, Hepatitis B or C. Subjects with serologic evidence of Hepatitis B vaccination (HepB surface Ab without the presence of HepB sAg) will be allowed to participate.
12. Herpes zoster or cytomegalovirus (CMV) that resolved less than 2 months before study enrollment. Subjects with a history of frequent outbreaks of Herpes Simplex Virus (defined as 4 or more outbreaks a year).
13. Clinically significant laboratory abnormalities at screening that, in the opinion of the Investigator, would make the subject a poor candidate for the study.
14. Subjects with absolute neutrophil count <1,000/mm³, or platelet count <50,000/mL.
15. Subject unable to comply with the following required washout periods:

Therapy/Medication	Washout Period
Systemic Therapies	
Disease Modifying Anti-Rheumatic Drugs (DMARDs), Biologics or immunosuppressants, such as: anakinra, adalimumab, azathioprine, corticosteroids, cyclosporine, etanercept, infliximab, methotrexate, TNF inhibitors, ustekinumab	1 month or 5 half-lives whichever is greater
Plaquenil	2 months
JAK inhibitors (oral or topical)	Prior or current treatment with a JAK inhibitor is prohibited at any time
Intralesional Steroids on the Scalp	1 month

	
Topical Treatments on the Scalp
 
Anthralin, bimatoprost, corticosteroids, diphenycprone, diphenylcycloprophenone (DPCP), Squaric acid dibutylester (SADBE), minoxidil, pimecrolimus, tacrolimus
	1 month
	Phototherapy, Laser Therapy, Excimer Laser	3 months

16. Participation in an investigational drug or device trial in which administration of an investigational study drug or device occurred within 30 days or 5 half-lives (whichever is longer) of Screening (Visit 1). Subjects who have participated in a study of an investigational drug, device or biologic agent for alopecia areata (AA, AU or AT) within 1 year of screening will be eligible to participate only with individual permission from the Medical Monitor.
 
17. Sensitivity to any of the ingredients in the study medications.
 
18. History of or current alcohol or drug abuse within 2 years of assessment for study enrollment.
 
19. Screening ECG findings of:
 
 • QTcF >450msec for males or >470msec for females (use of the ECG algorithm is acceptable for this purpose) • Heart rate < 45 or > 100 beats/minutes (inclusive) • Rhythm disturbance other than sinus arrhythmia or ectopic supraventricular rhythm (ectopic atrial rhythm) • Conduction disturbance including PR >240msec, pre-excitation (delta wave and PR <120msec), second degree or higher AV block • Acute or chronic signs of ischemia • Left Bundle Branch Block • Prior myocardial infarction 		

Duration of Treatment
 
Double-blind Treatment
 
Screening period up to 30 days.
 
Double-blind treatment period is 29 days (maximum of 28 days of study medication application).
 
Post-treatment Visit 16 is up to 33 days (30 +3 days) following Day 29 for subjects not continuing into the open-label extension.
 
Total study participation for subjects from Baseline (Visit 2) through Post-treatment Visit 16(Day 59 + 3 days) is up to 62 days (29 + 33).
 
Double-Blind + Open-Label Extension
 
The duration of the total study participation from Baseline (Visit 2) to Week 56 (Visit 16) is anticipated to be a maximum of 400 days (393 + 7 days).
 
The duration of the open-label extension (OLE) should be based on the date of the visit that the subject initiated OLE treatment rather than the days from Baseline (Visit 2). For subjects who entered the open-label extension and had a gap between Visit 7 and entry into the open-label extension due to an administrative delay total study participation may be longer than 400 days.
		

Endpoints
 
Pharmacokinetic:
 
Concentrations of ATI-50002 in the blood and ATI-50002 in the skin will be measured by a bioanalytical lab using fully validated analytical methods for the blood and qualified methods for the skin.
 
Pharmacodynamic:
		

Change from Baseline in the effects of ATI-50002 induced Janus kinase (JAK) 1/3 inhibition on the ALADIN scores, peribulbar infiltrate and other inflammatory biomarkers.

Safety:

Safety variables to be assessed include: adverse events, clinical laboratory tests (hematology, clinical chemistry, and urinalysis), vital sign measurements (systolic and diastolic blood pressures, respiration rate, heart rate, and oral body temperature), and electrocardiograms.

Efficacy Assessments:

Early signs of vellus hair regrowth are expected to take a minimum of 3 to 6 months in this population. Measurable terminal hair regrowth may take at least 6 months or longer.

Change from baseline in Severity of Alopecia Tool (SALT) score at Week 28 (Visit 13), Week 40 (Visit 14) and Week 52 (Visit 15).

Change from baseline in Alopecia Density and Extent Score (ALODEX) at Week 28 (Visit 13) Week 40 (Visit 14) and Week 52 (Visit 15).

Subject Satisfaction at Week 28 (Visit 13), Week 40 (Visit 14) and Week 52 (Visit 15).

Descriptive summaries of changes from entry into long-term open-label extension in CEA and SEA at Week 28 (Visit 13), Week 40 (Visit 14) and Week 52 (Visit 15) will be performed for those subjects with eyebrow loss.

Study Medication Administration

Double-blind Period: Subjects will apply a minimum of 1.5 mLs up to a maximum of 4 mLs of topical solution to the entire scalp twice-daily as directed.

Open-label Period: Subjects will apply a minimum of 1.5 mLs up to a maximum of 4 mLs of topical solution to the entire scalp twice-daily as directed. In addition, subject may apply a thin film of study medication to the entire affected eyebrow(s) twice-daily for up to 12 months.

Statistical Methods**Sample Size/ Power Calculations**

The planned sample size is 12 subjects.

Statistical Methods**Pharmacokinetic Analyses****Blood Samples**

Blood samples for analysis of the concentration of ATI-50002 will be taken from the first 6 subjects enrolled into the study at Day 1 (Visit 2) and Day 28 (Visit 6) at predose (0 hr), 1, 2, 4, 8 and on Day 2 (Visit 3) and Day 29 (Visit 7) at 24 hours post dose. For each subject, standard PK parameters will be calculated, based on the plasma concentrations of ATI-50002.

Scalp Biopsy

The concentration of ATI-50002 will be determined in a 4-mm punch biopsy of the scalp taken 24 hours post study medication application in the office on Day 2 (Visit 3) and Day 29 (Visit 7).

Pharmacodynamic (Biomarker) Analyses**ALADIN Scores**

The cytotoxic T lymphocyte infiltration (CTL), Interferon (IFN-gamma), and hair keratin (KRT) ALADIN scores will be calculated for each scalp biopsy sample as previously described in Xing et al, 2014, Jabbari 2016. Change in ALADIN scores within individual subjects will be assessed between Baseline (Visit 2), Day 29 (Visit 7) and Week 28 (Visit 13) for subjects enrolled into the open-label extension.

Histology

Scalp punch-biopsies will be formalin-fixed and paraffin-embedded and will be sectioned both vertically and horizontally by a qualified dermatopathologist. Specimens will be stained with hematoxylin and eosin (H&E) for routine histopathologic evaluation that will include (but is not limited to) diagnosis and evaluation of the presence, quantity, location, and quality of any hair, hair follicles, and inflammatory infiltrate present. Additionally, immunohistochemical (IHC) stains will be employed to identify immune cell populations (e.g., Lymphocytes, cytotoxic T-lymphocytes [CTLs]), and hair-specific keratins. IHC stains to assess inflammatory responses will include (but not be limited to) CD8, HLA-DR and ICAM-1. Data will be presented as percent change from baseline in the number of cells/ high power field in regions of interest (peribulbar areas) and in percent change from baseline in the number of cells/mm².

Blood for Immunology

Blood samples will be stained with cell surface antibodies for fluorescence acquisition cell sorting (FACS) analysis. FACS experiments will allow for assessment of the subset and activation status of immune cells involved in AA.

Safety Data

Safety analyses will include descriptive statistics calculated on the safety parameters using the safety population. The proportion of subjects with treatment-emergent adverse events will be tabulated and presented by treatment and Medical Dictionary for Regulatory Activities (MedDRA) System Organ Class. Vital signs and clinically significant abnormal laboratory results will also be tabulated and presented by treatment group. Overall incidence of adverse events will be compared between groups using a chi-square test.

Data from all randomized and treated subjects will be presented and summarized. Safety summaries by study treatment group will include listings by study medication of adverse events incidences within each MedDRA System Organ Class, and changes from pre-application values in vital signs. Adverse event summaries will be presented by study medication showing the proportion of subjects experiencing adverse events, both overall and by MedDRA System Organ Class.

TABLE OF CONTENTS

1. SYNOPSIS.....	8
2. LIST OF ABBREVIATIONS AND DEFINITIONS OF TERMS	18
3. INTRODUCTION	21
3.1. Summary	21
4. STUDY RATIONALE.....	24
4.1. Study Rationale	24
5. STUDY OBJECTIVE	25
5.1.1. Primary Objective	25
5.1.2. Secondary Objectives	25
6. SELECTION AND DISPOSITION OF STUDY POPULATION	26
6.1. Number of Subjects.....	26
6.2. Study Population Characteristics	26
6.3. Inclusion Criteria	26
6.4. Exclusion Criteria	26
6.5. Previous and Concomitant Medications and Therapies	28
6.5.1. Permitted Concomitant Therapies and Over the Counter Products (OTC)	28
6.5.2. Prohibited and/ or Restricted Medications	29
6.6. Subject Identifier (SI).....	30
6.7. Replacement Subjects	30
6.8. Subject Withdrawal Criteria	30
6.9. Study Termination.....	30
7. INVESTIGATIONAL PLAN.....	31
7.1. Overall Study Design	31
7.2. Study Procedures.....	32
7.3. Schedule of Assessments.....	33
7.4. Subject Nourishment.....	37
7.5. Duration of the Study	37
8. STUDY TREATMENT	37
8.1. Investigational Study Medication.....	37
8.2. Subject Randomization.....	38
8.3. Application of Study Medication.....	38
8.4. Study Medication Weights	39
8.5. Treatment Compliance	39

8.6. Dose Modification	39
8.7. Study Medication Accountability	40
8.8. Other Study Supplies	40
8.9. Blinding	40
8.9.1. Unblinding the Study Medication (Double-blind Period)	40
8.10. Study Medication Packaging, Labeling, Storage and Security	41
9. STUDY ASSESSMENTS	42
9.1. Efficacy Assessments	42
9.1.1. Severity Alopecia Tool (SALT) Score	42

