10. History of a serious local infection (*e.g.*, cellulitis, abscess) or systemic infection including but not limited to, history of treated (*e.g.*, pneumonia, septicemia) within 3 months prior to baseline (Visit 2). Subjects on an antibiotic for a non-serious, acute local infection must complete the course prior to enrollment into the study.
11. Positive for HIV, Hepatitis B or C. Subjects with serologic evidence of Hepatitis B vaccination (HepB surface Ab without the presence of HepB sAg) will be allowed to participate.
12. Herpes zoster or cytomegalovirus (CMV) that resolved less than 2 months before study enrollment. Subjects with a history of frequent outbreaks of Herpes Simplex Virus (defined as 4 or more outbreaks a year).
13. Clinically significant laboratory abnormalities at screening that, in the opinion of the Investigator, would make the subject a poor candidate for the study.
14. Subjects with absolute neutrophil count $<1,000/\text{mm}^3$ or platelet count $<50,000/\text{mL}$.
15. Subject unable to comply with the following required washout periods:

Therapy/Medication	Washout Period
Systemic Therapies	
Disease Modifying Anti-Rheumatic Drugs (DMARDs), Biologics or immunosuppressants, such as: anakinra, adalimumab, azathioprine, corticosteroids, cyclosporine, etanercept, infliximab, methotrexate, TNF inhibitors, ustekinumab	1 month or 5 half-lives whichever is greater
Plaquenil	2 months
	Prior or current treatment with a JAK inhibitor is prohibited at any time.

Therapy/Medication	Washout Period
Systemic Therapies	
JAK inhibitors (oral or topical)	
Intralesional Steroids on the Scalp	1 month
Topical Treatments on the Scalp	
Anthralin, bimatoprost, corticosteroids, diphenycprone, diphenylcycloprophenone (DPCP), Squaric acid dibutylester (SADBE), minoxidil, pimecrolimus, tacrolimus	1 month
Phototherapy, Laser Therapy, Excimer Laser	3 months

16. Participation in an investigational drug or device trial in which administration of an investigational drug or device occurred within 30 days or 5 half-lives (whichever is longer) of Screening (Visit 1). Subjects having participated in a study of an investigational drug, device or biologic agent for alopecia areata (AA, AU, AT) within 1 year of screening will be eligible to participate only with individual permission from the Medical Monitor.
17. Sensitivity to any of the ingredients in the study medications.

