10.2.4. Study Medication Interruption and Discontinuation

10.2.4.1 Study Medication Interruption

Treatment with ATI-50002 Topical Solution should be temporarily interrupted in the event of severe adverse events considered related to ATI-50002, or in the event of one or more of the abnormal laboratory values in Table 2.

Table 2: Study Medication Interruption Criteria

Laboratory Test	Hold Study Medication if:	Resume Study Medication if:
WBC count	< 2 x 10 ⁹ /L	≥ 2.5 x 10 ⁹ /L
ANC	< 1 x 10 ⁹ /L	≥ 1.5 x 10 ⁹ /L
Lymphocyte count	< 0.5 x 10 ⁹ /L	≥ 0.75 x 10 ⁹ /L
Platelet count	< 75 x 10 ⁹ /L	≥ 100 x 10 ⁹ /L
Hemoglobin	< 8 g/dL or decrease > 2 g/dL	≥ 10 g/dL
AST or ALT	> 3 x ULN	< 2 x ULN or within 20% of baseline values
Serum creatinine	>2 x ULN	<1.5 x ULN or within 10% of baseline value

If a subject has one or more of the abnormal laboratory values noted in Table 2, the investigator or designee upon receipt and review of the central laboratory report should instruct the subject to interrupt study medication applications. The investigator or designee should ask the subject about symptoms, concomitant illnesses and medications and repeat the test(s) as soon as possible. The Medical Monitor must be notified of dose interruptions due to SAEs considered related to study medication or laboratory abnormalities noted in Table 2.

If the retest confirms the abnormal laboratory value, then the study medication interruption should continue, followed by repeat testing once a week or sooner at the discretion of the investigator. The subject should be followed until the laboratory abnormality(s) return to normal or to baseline values. Study medication can be resumed after the abnormal lab value returns to normal or baseline, if in the opinion of the Investigator, it is in the best interest of the subject to continue.

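### Read as 50 × 10⁹/L, the platelet entry limit in exclusion criterion 14 is below the protocol's own 75 × 10⁹/L interruption limit and equals its permanent-stop limit

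*Protocol*

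**What the plan says.** Criterion 14 appears in the Protocol Synopsis and again, with the same numbers, in Section 6.4. It excludes subjects on two counts: "absolute neutrophil count <1,000/mm³" or "platelet count <50,000/mL".

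Section 10.2.4.1 governs on-study values: "Treatment with ATI-50002 Topical Solution should be temporarily interrupted" if any value in Table 2 occurs. For platelets, Table 2 gives a hold limit of below 75 × 10⁹/L and a resume limit of 100 × 10⁹/L or more. The investigator, "upon receipt and review of the central laboratory report should instruct the subject to interrupt study medication applications". Below the table is a second resumption condition: "Study medication can be resumed after the abnormal lab value returns to normal or baseline", subject to the investigator's view of the subject's best interest.

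Section 10.2.4.2 requires permanent discontinuation at platelets below 50 × 10⁹/L, or at a second occurrence below 75 × 10⁹/L, each confirmed by retest.

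Blood counts are drawn at Screening, Day 1, Day 15 and Day 29 of the double-blind period (Section 7.3).

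**The concern.** An entry limit and an interruption limit for the same laboratory test should not contradict each other. If a subject can be enrolled at a count that already calls for treatment to be held, the rule no longer separates a drug effect from the subject's usual level. The first on-study report then triggers an interruption that reflects the count at entry.

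In this trial the blinded period is 28 days and the planned arms are 8 and 4 subjects, so one uninformative interruption would be visible in a small safety and exposure summary. It would also expose to a JAK inhibitor a subject whom the protocol's own safety table regards as too low to continue dosing.

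**Working it through.** **Unit.** The criterion prints the platelet limit per mL. Taken literally, 50,000/mL × 10³ mL/L = 0.05 × 10⁹/L. Read per mm³, as the neutrophil limit beside it is written, 50,000/mm³ × 10⁶ mm³/L = 50 × 10⁹/L. The second reading is almost certainly what is meant, and a micro sign may have been lost when the PDF was read. Everything below uses 50 × 10⁹/L.

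**Limits side by side (× 10⁹/L).**

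| Rule | Source | Platelets | Neutrophils |
|---|---|---|---|
| Excluded at entry if below | Criterion 14 | 50 | 1,000/mm³ × 10⁶ mm³/L = 1.0 |
| Hold if below | Table 2 | 75 | 1.0 |
| Resume if at least | Table 2 | 100 | 1.5 |
| Stop permanently if below | 10.2.4.2 | 50 | 0.5 |
| Stop on second occurrence below | 10.2.4.2 | 75 | 1.0 |

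**Band that passes entry but meets the hold limit** (hold limit minus entry limit):
- Platelets: 75 − 50 = 25 × 10⁹/L, covering 50 to just under 75. The hold limit is 75/50 = 1.5 times the entry limit.
- Neutrophils: 1.0 − 1.0 = 0.

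**Entry limit relative to the first-occurrence permanent stop:**
- Platelets: 50/50 = 1.0, so there is no margin.
- Neutrophils: 1.0/0.5 = 2.0.

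The gap between entry and resume limits is not counted as a fault, because neutrophils show it too (entry 1.0, resume 1.5).

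**A subject with a steady count of 60 × 10⁹/L:**
1. Screening: 60 is not below 50, so criterion 14 is passed.
2. First on-study sample: 60 is below 75, so the interruption rule is met. On the text of Section 10.2.4.1 this could follow the Day 1 report; failing that, the Day 15 report.
3. Retest: 60 again, so the hold continues.
4. Resumption: if the Table 2 limit of 100 governs, a steady 60 never qualifies and the hold does not lift. If the sentence below the table governs, 60 is already the baseline value and treatment can resume.
5. After resumption: the next sample at 60 may count as a second occurrence below 75, which after retest means permanent discontinuation.

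On either reading of step 4, treatment can be interrupted or ended although the count has not changed since entry.

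**The case against.** Nothing in the protocol says that criterion 14 must mirror Table 2. Of the seven tests in that table, only neutrophils and platelets have a numeric entry limit. For the rest, screening relies on judgment: inclusion 7 on general health, exclusion 7 on hematological and coagulation disorders, exclusion 13 on clinically significant laboratory findings, and the mandatory review of screening results in Section 9.5.3. On this view criterion 14 is only a floor beneath that judgment, and an investigator would have to enrol knowingly a subject already below the hold limit. After enrolment there is a further check: "The Medical Monitor must be notified of dose interruptions" when they arise from a Table 2 abnormality.

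This stands as a reason to expect the case to be rare and the consequence small. It does not remove the inconsistency. The safeguards give no platelet number, the Section 9.5.3 review is made against entry criteria that include this limit, and notification comes after enrolment. Where the protocol does set a number, it should not admit a subject whom the next rule takes off treatment.

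Three stronger readings are tempting and are not supported:
- A reader might infer a thousandfold unit error from the printed per-mL unit. The intended unit is clear from context and the symbol may be an artefact of PDF reading, so no error is claimed from it.
- A reader might infer a miscalculation. No documented figure is computed wrongly; two rules are out of step.
- A reader might infer that the hemoglobin hold limits in Table 2 ("< 8 g/dL or decrease > 2 g/dL") overlap with the resume limit of 10 g/dL by a calculable amount. The table does not say what the decrease is measured from, the normal-or-baseline paragraph sits directly below it, and the laboratory's normal range is not given. No width can be established.

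**Conclusion.** The inconsistency is real and minor. With the limit read as 50 × 10⁹/L, criterion 14 admits a subject at 50 to just under 75 × 10⁹/L who already meets the interruption rule and may later meet the second-occurrence stopping rule with no drug effect. The neutrophil limit in the same criterion has no such gap, and the documents do not explain the difference.

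The conclusion rests on the unit reading and on the subject's count staying stable. The documents give no frequency for such candidates; they are assumed to be rare. No endpoint, sample-size figure or planned analysis changes. The hemoglobin wording merits at most an optional clarification.

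**What to change.** 1. In both the Synopsis and Section 6.4, state the platelet limit in × 10⁹/L and exclude counts below 75 × 10⁹/L at screening. The final value is for the sponsor's medical team.
2. Add that an on-study platelet value below 75 × 10⁹/L is handled under Section 10.2.4 and is not an entry-criterion withdrawal under Section 6.8. Without this sentence, raising the limit could turn one low value into both a hold and a reason for removal, because Section 6.8 lists loss of compliance with an entry criterion among the reasons for discontinuing a subject. Entry criteria are also rechecked before the open-label extension (Section 7.1), so the text should say which limit applies there.
3. Optionally, state that the hemoglobin decrease of more than 2 g/dL is from baseline, and that the Table 2 resume limits apply together with the sentence below the table.

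The cost is a wording amendment needing IRB approval and the rare loss of a candidate with platelets of 50 to just under 75 × 10⁹/L. No tests or visits are added.
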